6.9. Pharmacokinetic Analyses

6.9.1. Pharmacokinetic Parameter Estimation

Pharmacokinetic parameter estimates for LY3323795 will be calculated using standard noncompartmental methods of analysis.

The primary parameters for analysis will be C_{\max} and AUC of LY3323795. Other noncompartmental parameters, such as half-life ($t_{1/2}$), apparent clearance (CL/f), and apparent volume of distribution (V_D), may be reported.

Renal clearance of LY3323795 will be calculated as the ratio of amount excreted/AUC. This will be compared to the unbound glomerular filtration rate (GFR), which is estimated using creatinine levels.

In Part C, PK parameter estimates for itraconazole samples collected on Day 16 will be calculated using standard noncompartmental methods of analysis. Maximum concentration and AUC will be reported. Itraconazole concentrations collected as part of this study may be analyzed along with data collected in other studies as part of a larger assessment of itraconazole PK. If such an analysis is performed, the results of the analysis will be reported separately from the final report for this study. Concentrations of itraconazole metabolites may be characterized on an exploratory basis.

6.9.2. Pharmacokinetic Statistical Inference

In Part C, the area under the drug plasma concentration versus time from time zero to infinity ($AUC_{[0-\infty]}$) and C_{\max} for LY3323795 administered alone and in the presence of itraconazole will be compared using an analysis of variance (ANOVA) model. The parameters will be log-transformed prior to analysis. The model includes a fixed effect for the treatment and a random effect for subject. The following model will be built: $\ln(\text{PK parameter}) = \text{treatment} + \text{subject} + \text{random error}$, where treatment is a fixed effect with 2 levels: LY3323795 alone (reference) and LY3323795 with itraconazole (test).

The least square (LS) mean for each treatment and the 90% CI for the difference in means will be estimated from the ANOVA model and back-transformed from the log scale to provide estimates of the geometric means and 90% CIs for the ratio of the geometric means of LY3323795 + itraconazole versus LY3323795 alone.

The time to C_{\max} (t_{\max}) parameter will be analyzed using the Wilcoxon-signed rank test. Median differences and 90% CIs for the difference between LY3323795 + itraconazole (test) and the LY3323795 alone (reference) will be calculated.

6.10. Pharmacodynamics Analyses

6.10.1. Pharmacodynamics Parameter Estimation

In Parts A and B, plasma concentrations of $A\beta_{1-40}$ and $A\beta_{1-42}$ will be summarized for each dose group based on the C_{nadir} and the time to reach C_{nadir} (t_{nadir}).

In Part B, CSF concentrations of $A\beta_{1-40}$, $A\beta_{1-42}$ will be summarized for each dose group based on the C_{nadir} , t_{nadir} , and the 24-hour average values, expressed as a percentage change from baseline.

CCI

Other parameters may be calculated, as appropriate.

6.10.2. Pharmacodynamics Statistical Inference

For Part B of this protocol, statistical analysis of CSF $A\beta_{1-40}$, $A\beta_{1-42}$, CCI concentrations obtained over the fixed-scheduled sampling period will be analyzed using a repeated-measures analysis with the primary statistical inference of pairwise comparison of the overall mean difference among the LY3323795 doses and placebo using a 90% CI. The statistical model may include the baseline CSF $A\beta_{1-40}$ and $A\beta_{1-42}$ concentrations obtained during predose CSF collection period and fixed effects of dose groups (placebo and doses of LY3323795), scheduled CSF sampling time, and the interaction between dose groups and sampling times. A compound symmetric covariance structure may be used. From the statistical model, the primary statistical estimates will be the mean percentage reduction from baseline in CSF $A\beta_{1-40}$ and $A\beta_{1-42}$ concentrations at each time point with LY3323795 over the 36-hour sampling interval. The above model will fit both the log-transformed and percentage change from baseline in CSF $A\beta_{1-40}$ and $A\beta_{1-42}$ concentrations.

Additional exploratory analysis will be performed on plasma concentrations of TMEM27 with a similar statistical model.

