**Statistical Analysis:**

The sample size for Part A is customary for Phase 1 studies evaluating safety, PK, and/or PD parameters, and is not based on statistical mean estimation. Parts B and C are not formally powered to detect a prespecified anticipated effect; however, precision intervals have been calculated to show what may be observed for changes in cerebrospinal fluid (CSF) A $\beta$  and effect of itraconazole on LY3323795 given the sample sizes.

No formal interim analyses are planned for this study. Interim access to data (IAD) is scheduled to occur throughout the study. The purpose of these IAD reviews is to examine the safety and or PK/PD data and guide dose selections.

All investigational product and protocol procedure adverse events will be listed, and if the frequency of events allows, safety data will be summarized using descriptive methodology. Safety laboratory parameters, vital signs, and electrocardiogram parameters will be listed and summarized using standard descriptive statistics for values at each time point as well as changes from baseline.

PK parameter estimates for LY3323795 will be calculated using standard noncompartmental methods of analysis. The primary parameters for analysis will be Cmax and AUC of LY3323795. Other noncompartmental parameters, such as half-life, apparent clearance, and apparent volume of distribution may be reported.

For Parts A and B, plasma concentrations of A $\beta$ 1-40 and A $\beta$ 1-42 will be summarized for each dose group based on the nadir concentration (Cnadir) and the time to reach Cnadir (tnadir).

In Part B, CSF concentrations of A $\beta$ 1-40, A $\beta$ 1-42, and CCI will be summarized for each dose group based on the Cnadir, tnadir, and the 24-hour average values, expressed as a percentage change from baseline. Statistical analysis of CSF A $\beta$ 1-40 and A $\beta$ 1-42 concentrations obtained over the fixed-scheduled sampling period will be analyzed using a repeated-measures analysis with the primary statistical estimation of the overall mean percentage change from baseline and 90% confidence interval among the LY3323795 doses and placebo at each post dose time point.

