In healthy subjects, CSF indwelling catheter studies conducted by Lilly have shown increases in CSF A $\beta$  concentration over 24 to 40 hours of sampling (Lucey et al. 2015). In these CSF catheter studies, the initial 4-hour sampling interval following the catheter placement showed a 10% to 15% increase in A $\beta$  concentration. Subjects receiving placebo following the catheter placement showed additional increases of 20% to 30% over a 36-hour CSF sampling period. Similar findings were shown by Bateman (2008). Therefore, placebo will also be included in Part B of this study. Previous studies have also shown that CSF A $\beta$  concentrations slowly return to baseline following a treatment that disrupts A $\beta$  synthesis; however, due to the large variability in CSF A $\beta$  concentrations both within and between individuals, a long duration of sampling is required to fully characterize the PD time course.

An assessment of LY3323795 PK with concomitant itraconazole administration is planned in Part C. In vitro recombinant CYP isoform phenotyping studies indicate CYP3A4 is the only tested CYP isoform that metabolizes LY3323795. In vitro metabolism studies with human hepatocytes suggest that CYP-mediated metabolism accounts for approximately 70% of the overall metabolism in hepatocytes. Taken together, these data result in a predicted LY3323795 AUC increase of approximately 4-fold when LY3323795 is coadministered with the strong CYP3A inhibitor itraconazole. Accordingly, coadministration with itraconazole will help determine the clinical relevance of CYP3A inhibition on LY3323795 clearance. The dosing regimen for itraconazole was optimized using a physiologically based PK model with the goal of reaching steady-state concentrations as rapidly as possible (Ke et al. 2014). The use of the oral solution formulation of itraconazole is specified as it has higher bioavailability and less variability in absorption than solid dosage formulations.

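### Part B CSF Aβ: no placebo-corrected estimate or CI is defined at any time point, although earlier studies saw placebo CSF Aβ rise 20% to 30% over 36 hours

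*SAP*

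**What the plan says.** SAP 6.10.2 and protocol 10.3.3.2 use nearly the same text. Both call for a repeated-measures analysis of CSF Aβ1-40 and Aβ1-42 in Part B and name two outputs as primary:

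- The primary inference is a "pairwise comparison of the overall mean difference among the LY3323795 doses and placebo using a 90% CI".
- From the same model, "the primary statistical estimates will be the mean percentage reduction from baseline in CSF" Aβ at each time point with LY3323795 over 36 hours. Placebo is not mentioned here.

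The model terms are permissive: "The statistical model may include the baseline CSF" Aβ values from the predose period and "fixed effects of dose groups (placebo and doses of LY3323795), scheduled CSF sampling time, and the interaction between dose groups and sampling times". Two scales are planned and neither is said to lead: "The above model will fit both the log-transformed and percentage change from baseline in CSF" Aβ.

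The protocol synopsis (Statistical Analysis) words the target differently, as the "overall mean percentage change from baseline and 90% confidence interval among the LY3323795 doses and placebo at each post dose time point". This puts placebo at each time point but states no difference from it.

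On drift, protocol 5.4 says: "Subjects receiving placebo following the catheter placement showed additional increases of 20% to 30% over a 36-hour CSF sampling period". It then concludes: "Therefore, placebo will also be included in Part B of this study".

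**The concern.** Protocol 3.1 treats the fall in CSF Aβ as the study's most important biomarker and intends the data to help choose doses for later studies. Protocol 5.4 says that long sampling is needed to describe the time course, and that placebo is there because Aβ rises without drug. No planned estimate brings these two purposes together: the overall contrast removes drift but has no time course, and the time-point estimates do the opposite. SAP 6.10.1 does not fill the gap, because its nadir and 24-hour-average summaries are also changes from baseline.

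A reader who takes the own-baseline curve as the drug effect would see that effect fade faster at late times than it does.

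**Working it through.** **Inputs.** Placebo rise of 20% to 30% over 36 h (protocol 5.4). Post-dose CSF times of 1 to 10, 12, 14, 16, 18, 20, 24, 28, 32 and 36 h (protocol section 2, Part B schedule): 19 samples, 15 of them at or before 20 h. Five subjects per dose, two placebo per cohort and SD 22% (SAP 5.1); three cohorts give 6 pooled placebo subjects.

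**The plan's own figure.** SAP 5.1 gives a half-width of 21% for the 80% CI with about 90% coverage. It reproduces: t(0.90, 4 df) × 22 × √(χ²(0.90, 4 df)/4)/√5 = 1.533 × 22 × √(7.779/4)/2.236 = 21.04. This is a one-sample change from baseline. It contains no placebo term, so it does not describe a placebo contrast.

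**Bias of the own-baseline reading.** Assume, since the documents do not say, that drift is linear, x(t) = d·t/36 with d = 0.20 or 0.30, that it acts proportionally under treatment, and that the true reduction versus placebo, e, is constant. Then the treated change from baseline is (1−e)(1+x) − 1, and the own-baseline reduction falls short of e by (1−e)x.

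| True reduction e | Shortfall at 10 h, points (d = 20% / 30%) | 24 h | 36 h |
|---|---|---|---|
| 50% | 2.8 / 4.2 | 6.7 / 10.0 | 10 / 15 |
| 70% | 1.7 / 2.5 | 4 / 6 | 6 / 9 |
| 90% | 0.6 / 0.8 | 1.3 / 2 | 2 / 3 |

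So a true 50% reads as 43.3% / 40.0% at 24 h and 40% / 35% at 36 h. The 19 times sum to 255 h, a mean of 13.42 h. The mean shortfall at e = 50% is therefore 50 × d × 13.42/36 = 3.7 / 5.6 points.

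**Range over other drift forms.** If the drug does not reduce the drift at all (additive), the shortfall is x itself: 13.3 / 20 points at 24 h and 20 / 30 at 36 h. If the rise is proportional but complete by 12 h, the shortfall at 10 h for e = 50% is 50 × d × 10/12 = 8.3 / 12.5 points. If the rise starts only after 24 h, it is zero until then.

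**Which scale corrects for drift.** Under proportional drift the log ratio to placebo is ln[(1−e)(1+x)/(1+x)] = ln(1−e), so it recovers e exactly. The difference in percentage change is (1−e)(1+x) − 1 − x = −e − e·x, which overstates the effect by e·x: a true 50% shows as 60 / 65 points at 36 h. Under additive drift this reverses. The percentage-change difference gives 50 points, while the log ratio gives 1 − 0.7/1.2 = 41.7% or 1 − 0.8/1.3 = 38.5%.

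**Precision.** All cases below use t(0.95, 17 df) = 1.740.

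- Percent scale, SD 22 in all groups: own-baseline half-width 1.740 × 22/√5 = 17.1 points; contrast 1.740 × 22 × √(1/5 + 1/6) = 23.2 points.
- Log scale, assuming a log SD of 0.22 (not in the documents): contrast half-width 1.740 × 0.22 × 0.6055 = 0.232, so a 50% reduction has a 90% CI of 37% to 60%. For the own-baseline estimate, 1.740 × 0.22/√5 = 0.171 gives 41% to 58%.
- If the SD stays at 22 points of baseline when half the Aβ remains, the log SD is nearer 22/50 = 0.44. Applied to both groups as a pessimistic case, the half-widths double to 0.463 and 0.342, and the intervals become 21% to 69% and 30% to 64%.

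**The case against.** The strongest reply is that the two outputs do not conflict. Inference and estimates can be read as complementary products of one model: an overall comparison, and time-point means beside it. That reading is fair, and the documents do not rule it out. The synopsis already lists placebo at each time point, and SAP 6.10.1 summarises CSF change for each dose group, so a reader could set the placebo curve beside the treated ones. With the interaction term in the model, the contrast is a simple combination of means already planned. Without it, the overall contrast serves for every time point. What stands against this is narrow: the interaction is optional, and no difference or interval is defined at any time point.

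The context also limits the point. The objective is secondary and exploratory, and SAP 6.1 rules out formal testing and allows further analyses. The listed endpoint is the nadir as percentage change from baseline, and the larger biases fall at 24 to 36 h. At 10 h the linear case gives 2.8 / 4.2 points against an own-baseline half-width of 17. SAP 6.11 plans an indirect-response model for CSF Aβ1-40, but does not mention drift and does not commit to reporting the results in the study report. The 20% to 30% is a finding from earlier studies, not a forecast for this one.

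Three stronger readings are tempting and are not supported:

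- A reader might infer two rival primary endpoints. The text allows the complementary reading above.
- A reader might infer that any placebo contrast beats the own-baseline figure. On the percentage-change scale under proportional drift, the contrast's bias is e·x against (1−e)x. For reductions of 50%, 70% and 90% it is at least as biased and more variable, so it has the larger mean squared error at all 19 times.
- A reader might infer that the goal in protocol 5.1.2.1 of more than 50% reduction relative to baseline contradicts 5.4. A goal stated relative to baseline does not.

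**Conclusion.** The concern holds in a limited form. Drift is the protocol's own reason for the placebo arm, yet the only time-resolved estimates specified are own-baseline reductions, and no placebo-corrected estimate or CI is defined at any time point. For a true 50% reduction under linear, proportional drift, the cost is 6.7 to 10 points at 24 h, 10 to 15 at 36 h, and 3.7 to 5.6 on average over the schedule. It shrinks to 2 to 3 points at 36 h for a 90% reduction, and could reach 20 to 30 points there if drift is additive. The documents give neither the shape of the drift nor its behaviour under treatment, so these figures illustrate size and do not predict it. Severity is minor: a cheap improvement to an exploratory secondary analysis.

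**What to change.** In SAP 6.10.2, protocol 10.3.3.2 and the synopsis:

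1. Make the dose-group-by-time term definite.
2. Add contrasts of each LY3323795 dose with pooled placebo, with 90% CI, at each scheduled time point. Take them from the log-transformed fit already planned and back-transform to a percentage reduction versus placebo, as SAP 6.9.2 does for the Part C ratio.
3. Keep the overall contrast, and keep the own-baseline changes for every group, placebo included, labelled as not corrected for drift.
4. Report the percentage-change contrast as a sensitivity analysis only, and state that it overstates the effect under proportional drift while the log ratio understates it under additive drift.

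The cost is wording; the samples, the model and both scales are already planned. The price is precision: about 23 against 17 points on the percent scale, or 37% to 60% against 41% to 58% around a 50% reduction with a log SD of 0.22. It is wider still if fewer than three cohorts run and the placebo pool is smaller. That is why the contrasts should accompany the own-baseline estimates and not replace them.

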6.11. Pharmacokinetic/Pharmacodynamic Analyses

It is intended that a compartmental modeling approach will be used to describe the plasma and CSF PK and CSF PD of LY3323795. Compartmental modeling will be performed using nonlinear mixed-effects modeling. Although it is not intended that the model will assess the impact of patient-specific factors (such as age, body weight, or race/subrace) on LY3323795 PK, these may be included, if appropriate. Modeling may be performed sequentially by first modeling plasma PK and then fixing the values from that model when developing a model to describe CSF PK. It is intended that an indirect response model will be used to characterize the PD effect of LY3323795 on CSF $A\beta_{1-40}$ formation, with PK parameters fixed to those values determined in previous steps. Other PD endpoints (eg, $A\beta_{1-42}$) may be modeled, if warranted.

Other modeling approaches or graphical analyses may be used, as deemed appropriate. The results of this modeling may not necessarily be included in the final study report.

Further details on the planned pharmacokinetic analyses can be found in the pharmacokinetic analysis plan.

6.12. Interim Analyses and Data Monitoring

No interim analyses are planned for this study. If an unplanned interim analysis is deemed necessary, the Lilly clinical pharmacologist, clinical research physician (CRP)/investigator, or designee will consult with the appropriate medical director or designee to determine if it is necessary to amend the protocol.

Safety and/or PK Interim Access to Data (IAD) reviews are scheduled to occur throughout the study. The purpose of these IAD reviews is to examine the safety data and guide dose selections.

In Part A, the investigator and the Lilly clinical pharmacologist/CRP/study team will make the determination regarding dose escalation based on their review of the safety and tolerability data, along with PK data, as applicable

In Part B, dose selection will be based on PK/PD data.

The investigator will remain blinded and the Lilly clinical pharmacologist/CRP/study team will be unblinded during these IAD reviews.

Additional IAD reviews may be conducted at any time throughout the study, as required, to ensure subjects' safety or to help guide dosing. An assessment committee will not be formed.

6.13. Clinical Trial Registry Analyses

Additional analyses will be performed for the purpose of fulfilling the Clinical Trial Registry (CTR) requirements.

Analyses provided for the CTR requirements include the following:

Summary of AEs, provided as a dataset which will be converted to an XML file. Both Serious Adverse Events and "Other" Adverse Events are summarized by treatment group and by MedDRA Preferred Term.

- An adverse event is considered "serious" whether or not it is a treatment emergent adverse event (TEAE).
- An adverse event is considered in the "Other" category if it is both a TEAE and is not serious. For each SAE and "Other" AE, for each term and treatment group, the following are provided:
 - the number of participants at risk of an event
 - the number of participants who experienced each event term

- the number of events experienced.
- Consistent with www.ClinicalTrials.gov requirements, “Other” AEs that occur in fewer than 5% of patients/subjects in every treatment group may not be included if a 5% threshold is chosen (5% is the minimum threshold).
- Adverse event reporting is consistent with other document disclosures (for example, the clinical study report [CSR], manuscripts, and so forth)
